
TEST PRODUCT, DOSE, AND ROUTE OF ADMINISTRATION
	
Over-encapsulated azithromycin tablets will be provided during the randomized period of the study. Azithromycin will be dosed as one 500 mg capsule three times per week.
 
During the open-label extension period, azithromycin 500 mg tablets (without over-encapsulation) will be provided by the site pharmacy and dosed three times per week.

CONTROL PRODUCT, DOSE AND ROUTE OF ADMINISTRATION	Placebo, matching the appearance of the azithromycin capsules and comprised of the same capsule material as the test product will be provided during the randomized period of the study. Placebo will be dosed as one capsule three times per week.
STANDARD OF CARE TREATMENT: TISP	In this study, TISP is given as standard of care, will be based on clinical prescription for 28 days on, followed by 28 days off, and will conform to manufacturer administration guidelines.

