#### 8.5.1 Dosage/Dosage Regimen

Randomized study drug (azithromycin or placebo) and open-label azithromycin will be taken by mouth three times weekly during the following study periods:

- Treatment V1-V2: azithromycin or placebo without TISP: 14 days
- Treatment V2-V3: azithromycin or placebo with TISP: 28 days

Subjects participating in the optional open-label extension:

- Treatment V3-V4: azithromycin without TISP: 28 days
- Treatment V4-V5: azithromycin with TISP 28 days

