## 10 EVALUATIONS BY VISIT

### Randomized Period

#### 10.1 Visit 1 – Day -14

\*A respiratory culture may be obtained prior to randomization to confirm eligibility criteria #4. If a respiratory culture is needed, the remaining Visit 1 procedures should be completed after confirming positive *Pa* culture results.

1. Review the study with the subject (subject's legal representative) and obtain written informed consent and HIPAA authorization and assent, if appropriate.
2. Assign the subject a unique study number.
3. If there is not a recent respiratory culture available, obtain culture to confirm eligibility:
  - Review culture results.
  - If *Pa* positive and meets criteria #4, schedule subsequent visit to complete remaining Visit 1 procedures.
  - If *Pa* negative, record as Screen Fail.
4. Review and record previous use of azithromycin and inhaled tobramycin.
5. Record demographics and CFF Registry ID, if consent obtained.
6. Record medical history, including a history of CF diagnosis and date.
7. Record concomitant medications.
8. Administer PRO questionnaires (CFRSD-CRISS and CFQ-R).
9. Perform a complete physical examination.
10. Measure and record height and weight.
11. Obtain and record vital signs.

12. Perform and record spirometry.
13. Collect blood or urine for pregnancy test (if female of child-bearing potential).
14. Obtain resting ECG.
15. If able to expectorate sputum, collect expectorated sputum.
16. Confirm subject eligibility.
17. Randomize to study drug.
18. Dispense study drug.
19. Review study drug dose and schedule with subject.
20. Provide subject diary and instructions for completion.
21. Remind subject to NOT use inhaled tobramycin between this day and Visit 2.
22. Instruct subject to bring study drug bottle, any remaining capsules, and diary to Visit 2.
23. Schedule subject for Visit 2.

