### 15.4 Analysis of Secondary Endpoints

#### Randomized Period

Descriptive analyses and graphical displays will be used to summarize all secondary endpoints. Endpoints will be compared between the azithromycin and placebo treatment groups from Visit 1 through Visit 3.

All reported SAEs and AEs will be coded using MedDRA and grouped by body system. The incidence of AEs (including emergent abnormal QTc parameters) between the azithromycin and placebo treatment groups will be tabulated by seriousness, severity, and relationship to study drug. Rates of (S)AEs by System Organ Class (SOC) will also be summarized. Poisson regression modeling will be used to derive rate ratios and corresponding 95% confidence and to compare groups using a two-sided 0.05 level test. Histograms showing the frequency of the number of (S)AEs in each treatment group will be included.

The proportion of subjects permanently or temporarily discontinuing study drug will also be tabulated by treatment group. Drug discontinuation events will be categorized as: (1) Permanently discontinued study drug, (2) Permanently discontinued study drug and withdrew from study, and (3) Temporarily discontinued study drug. Reason for permanent drug discontinuation will be summarized. Compliance measures will be computed separately for the TISP and azithromycin /placebo therapies.

Continuous secondary endpoints including changes in sputum bacterial density, weight, patient-reported quality of life (as measured by scales derived from the CFQ-R and CFRSD-CRIS), and pulmonary function (FEV1 % predicted, FVC, and FEF25%-75%) will be modeled similarly to the primary endpoint. Predicted values for spirometry measures at each visit will be calculated using the Global Lung Initiative reference equations. Least squares means and the treatment effect for the change for each secondary endpoint from Visit 1 to Visit 3 will be presented as well as corresponding 95% confidence intervals and p-values. The relative change in FEV1(liters) during administration of TISP from Visit 2 to Visit 3 will be analyzed in a similar manner.

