Between Visit 1 (Day -14) and Visit 2 (Day 0), a two-week run-in period will be used to begin administration of either azithromycin or placebo. Among those randomized to azithromycin, the 2-week run-in period will be used to initiate azithromycin and standardize uptake prior to the start of the next TISP cycle. Among those randomized to placebo, the run-in period will be used as a standardized washout prior to the start of the next TISP cycle. Subjects will begin TISP at Visit 2 in addition to their continued dosing of randomized study drug treatment (azithromycin or placebo). Subjects will continue both TISP and study drug dosing for 28 days (up until Visit 3), which corresponds with the end of a clinically prescribed 4-week cycle of TISP. Subjects completing the study through Visit 3 (Day 28) will be offered participation and consent to an 8-week open-label extension period during which azithromycin will be provided. During the open-label period, subjects will be instructed to remain off of TISP for the first 4-week period, followed by a 4-week period of TISP. Total duration of subject participation will be up to 6 weeks for those enrolled in the randomized study and up to 98 days for subjects participating in the optional open-label extension. Subjects who meet all inclusion criteria and none of the exclusion criteria will be eligible for the study.

The primary objective of this study is to determine if azithromycin impairs the previously-recognized clinical benefits of inhaled tobramycin by comparing changes in pulmonary function as measured by FEV₁ between subjects randomized to azithromycin versus placebo.

The secondary objectives for the randomized period are to:

- Compare changes in patient-reported quality of life between subjects randomized to azithromycin versus placebo

The secondary exploratory objectives for the randomized period are to:

- Compare the safety profile between subjects randomized to azithromycin versus placebo
- Compare changes in additional spirometry measures, bacterial density, and weight between subjects randomized to azithromycin versus placebo
- Compare rates of pulmonary exacerbations, hospitalizations, and acute antibiotic usage between subjects randomized to azithromycin versus placebo

The objectives for those continuing in the open-label extension:

- Among those randomized to azithromycin and remaining on azithromycin, obtain additional data to determine the long term effect of azithromycin on clinical outcomes

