Study drug compliance (azithromycin or placebo) is summarized in terms of the protocol defined treatment regimen during the randomized period. Compliance percentage is calculated for each participant as the number of doses reported taken divided by the number of doses expected (three 500 mg capsules per week over the six-week period, i.e. 18 doses), multiplied by 100. Also summarized is the compliance with TIS/TIP, calculated in a similar manner and assuming that the expected number of doses is 84 (inhaled twice daily over the six-week period). The average drug compliance is summarized in each treatment group. Also shown is the number and percentage of participants with $\geq 80\%$ compliance.

The number of participants included in the per-protocol population is provided by treatment group and reasons for exclusions are listed. Per-protocol population is defined as all randomized

participants having completed $\geq 80\%$ of doses of study drug (azithromycin or placebo) and who did not require the use of acute antibiotics or steroids.

A.4 Summary of Adverse Events

The safety population is used in all summaries of adverse events (AEs) and serious adverse events (SAEs). Note that all tables summarizing AEs also include SAEs (which are a subset of the AEs) unless otherwise specified.

According to our regulatory reporting criteria, a pulmonary exacerbation requiring a hospitalization results in an SAE (regardless of its expectedness). For the TDN trials, sites are asked to record the symptoms or physical findings associated with the pulmonary exacerbation as individual adverse events and to designate the seriousness of each of these events. Thus a single pulmonary exacerbation can be reported as several SAEs.

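### SAP A.3 expects 84 tobramycin doses in a randomized period that schedules 28 days (56 doses), so full adherence would be reported as 67%

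*SAP*

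**What the plan says.** SAP Appendix A.3 (Summary of Protocol Adherence Measures) defines compliance as doses reported taken, divided by doses expected, times 100. For study drug the expected number is 18, three capsules a week for six weeks. For TIS/TIP the calculation is to be done in the same way, "assuming that the expected number of doses is 84 (inhaled twice daily over the six-week period"). A.3 then adds: "Also shown is the number and percentage of participants with" at least 80% compliance, without naming a drug. Protocol 15.4 states: "Compliance measures will be computed separately for the TISP and azithromycin /placebo therapies".

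On when tobramycin is taken, the two documents agree:

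- SAP 1.1 has tobramycin start at Visit 2 and continues: "Subjects will continue both TISP and study drug dosing for 28 days (up until Visit 3").
- Protocol 8.5.1 lists "Treatment V1-V2: azithromycin or placebo without TISP: 14 days" and then "Treatment V2-V3: azithromycin or placebo with TISP: 28 days".
- Protocol 10.1, in the Visit 1 procedures, instructs staff: "Remind subject to NOT use inhaled tobramycin between this day and Visit 2".
- The protocol synopsis says standard-of-care tobramycin "will be based on clinical prescription for 28 days on, followed by 28 days off".
- Protocol 8.9.1 describes twice-daily inhalation for both the solution and the powder.

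**The concern.** A.3 appears to have carried the six-week study-drug period over to a drug that is scheduled for only four of those weeks. The denominator therefore contains 14 days of doses that participants are told not to take.

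Tobramycin is the background therapy that the primary objective concerns. If the trial shows no difference between arms, or a small one, the first question will be whether participants took their tobramycin, and the A.3 compliance summary is the planned answer. With 84 as the denominator, both arms would appear to have taken at most about two thirds of it. A reader could wrongly put the result down to poor background adherence.

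The denominator also rewards the wrong behaviour. Someone who used tobramycin twice daily through the run-in as well, against the Visit 1 instruction, would score 84/84 = 100%. Someone who followed the schedule exactly would score 66.7%.

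**Working it through.** **Inputs**

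- Frequency: twice daily (SAP A.3; protocol 8.9.1 for both formulations).
- Period used in A.3: six weeks, 42 days.
- Scheduled tobramycin period: 28 days, Visit 2 to Visit 3 (SAP 1.1; protocol 8.5.1).
- Stated window on the Visit 2 to Visit 3 interval: -2/+4 days, so 26 to 32 days (protocol synopsis, duration of participation).
- Compliance = doses taken / doses expected x 100 (SAP A.3).

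**The plan's own figures**

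- Tobramycin: 2 x 42 = 84. This reproduces A.3, but only by including the 14 run-in days without tobramycin.
- Study drug: 3 x 6 = 18. This agrees with A.3, and the six-week basis is consistent with the study-drug schedule.

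**Other bases that might explain 84**

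- Powder capsules at 4 per inhalation: 8 x 28 = 224.
- Randomized and open-label tobramycin cycles together: 2 x 56 = 112.

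Neither gives 84.

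**Expected doses on the documented schedule**

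2 x 28 = 56.

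**What A.3 would report with 84 as denominator**

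| Actual tobramycin use | Doses | Reported compliance |
|---|---|---|
| Full use, 28 days | 56 | 56/84 = 66.7% |
| 80% of 56 (44.8, rounded up) | 45 | 45/84 = 53.6% |
| Full use, 26-day interval | 52 | 52/84 = 61.9% |
| Full use, 32-day interval | 64 | 64/84 = 76.2% |

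**The 80% line**

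0.8 x 84 = 67.2, so 68 doses are needed, which is 34 days of twice-daily use. That is longer than the 28-day cycle and longer than the longest stated interval of 32 days. It could be met only if Visit 2 fell two days early and Visit 3 four days late against their nominal days, with dosing throughout: Day -2 to Day 32 is 34 days, and 68/84 = 81.0%. At the opposite extreme, Day 4 to Day 26 is 22 days, and full use reads 44/84 = 52.4%.

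**The case against.** The strongest case is that little depends on this number. No planned test, model or stopping rule uses tobramycin compliance. The per-protocol set is defined by study-drug doses and by the use of acute antibiotics or steroids. The same constant divides both arms, so their relative comparison is unchanged, and mean compliance can be recovered by multiplying by 84/56 = 1.5. SAP 2.3 also lets the final report describe and justify deviations from the plan. All of this stands, and it limits the severity. It does not make the number right: a programmer who follows A.3 produces a wrong summary, and one who corrects it has a deviation to explain.

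Second, the 80% sentence names no drug, and the only 80% criterion defined elsewhere is for study drug. Protocol 15.4 asks for separate compliance measures but sets no threshold for tobramycin. This also stands, so an empty 80% category for tobramycin is a conditional consequence. The position of the sentence, directly after the tobramycin calculation and the average compliance, makes that reading likely but not certain. The 66.7% figure does not depend on it.

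Third, a fixed 56 is not perfect. If dosing runs to the actual Visit 3 instead of stopping at 28 days, full use over 26 to 32 days would read 52/56 = 92.9% to 64/56 = 114.3%. That is true of any fixed denominator, including the 18 used for study drug. A sentence on values above 100% would deal with it.

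**Conclusion.** The concern holds. The figure of 84 contradicts the SAP's own design section and the protocol, both of which schedule 28 days of tobramycin in the randomized period. At twice daily the expected number is 56, and full adherence would be reported as 66.7%, an understatement of one third in both arms. This rests on the 28-day cycle and on the twice-daily frequency that A.3 itself uses. Across the stated 26 to 32 day interval, full use would read 61.9% to 76.2%, so the understatement does not depend on visit timing within that window.

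If the 80% count is meant to include tobramycin, it would be close to zero by construction. That part is conditional on how an ambiguous sentence is read.

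The effect is limited to a descriptive adherence summary, and the primary and per-protocol efficacy analyses are untouched. It should be fixed because the summary bears directly on how the primary result is interpreted, and the correction is very small.

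**What to change.** In SAP A.3, reconcile the TIS/TIP denominator with the 28-day Visit 2 to Visit 3 period stated in SAP 1.1 and protocol 8.5.1, which gives 56 expected doses in place of 84. State that the 80% count is given separately for study drug (of 18) and for TIS/TIP (of 56), in line with protocol 15.4, or else that it applies to study drug only. It would help to add how values above 100% are handled when the visit interval exceeds 28 days.

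The cost is one number and a clarifying phrase. No new data are needed: the daily diary already captures tobramycin doses (protocol 8.8 and 9.1.12), and tobramycin use is recorded at Visit 3 (protocol 10.3). The dosing schedule and the per-protocol definition stay as they are.

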Event rates for hospitalization, pulmonary exacerbations, intravenous antibiotic usage, inhaled antibiotic usage, and oral antibiotic usage from Visit 1 through Visit 3 will be descriptively summarized and differences in the proportions of subjects with an event between the treatment groups will be estimated with accompanying 95% confidence intervals. Event rates will be compared between treatment groups using Poisson regression.

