The incidence of AEs (including emergent abnormal QTc parameters) between the azithromycin and placebo treatment groups is tabulated by seriousness, severity, and relationship to study drug. The proportion of participants with at least one (S)AE, the average number of (S)AEs per patient, and the rate of (S)AEs per day of follow-up are reported. Poisson regression modeling is used to derive rate ratios and corresponding 95% confidence and to compare groups using a two-sided 0.05 level test. The difference in the proportion of participants experiencing at least one (S)AE between treatment groups is also reported, with corresponding 95% confidence intervals calculated using the Newcombe-Wilson method and p-values derived from a Fisher's exact test. Histograms showing the frequency of the number of (S)AEs in each treatment group are included.

All reported SAEs and AEs are coded using MedDRA and grouped by body system. Detailed summary tables of individual (S)AEs grouped by SOC are included to show the number and percent of participants experiencing each (S)AE by treatment group. The number and rate of events for each (S)AE is also reported by treatment group. Poisson regression is used to derive rate ratios and corresponding 95% confidence intervals comparing treatment arms for each SOC. Treatment groups are compared by the proportion of participants experiencing (S)AEs by System Organ Class (SOC) as well as the difference in proportions with corresponding 95% confidence intervals to compare treatment arms.

All SAE narratives are included in a listing appended to this report.

A.5 Summary of Spirometry Results

The primary endpoint is the difference between the azithromycin and placebo treatment groups in the relative change from Visit 1 to Visit 3 in FEV1 (liters). The primary efficacy analysis is conducted on the m-ITT population and repeated on per-protocol population. Predicted values for spirometry measures at each visit are calculated using the Global Lung Initiative reference equations.

A linear regression model adjusted for randomization strata is used to compare the primary endpoint between treatment groups. Least squares means and the treatment effect are presented

along with corresponding 95% confidence intervals and p-values. The primary analysis is adjusted for the group sequential monitoring.

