The number of pulmonary exacerbations and hospitalizations is descriptively summarized. Proportions of participants initiating intravenous, inhaled, and oral antibiotics during randomized period are also presented. The differences in the proportions of participants experiencing at least one event between treatment groups are estimated with accompanying 95% confidence intervals calculated using the Newcombe-Wilson method and p-values derived from a Fisher's exact test.

A.7 Summary of Weight

Mean changes in weight (kg) from Visit 1 to each post-randomization visit for both treatment groups during the randomized period are summarized descriptively in a figure. 95% confidence intervals (using t-distribution approximation) are included at each time point. The number of participants at each time point is included in a legend below the figure.

A linear regression model adjusted for randomization strata is used to compare changes in weight (kg) between treatment groups. Least squares means and the treatment effect are presented along with corresponding 95% confidence intervals and p-values.

The weight (kg) is also summarized at each study visit during the randomized period and as a change from Visit 1 and Visit 2. The differences between treatment groups are presented with accompanying 95% confidence intervals and p-values calculated using two-sample t-tests.

A.8 Summary of Patient-Reported Quality of Life Measures

Mean changes in CFRSD-CRISS and CFQ-R Respiratory Symptom Scale (RSS) from Visit 1 to each post-randomization visit for both treatment groups during the randomized period are summarized descriptively in figures. 95% confidence intervals (using t-distribution approximation) are included at each time point. The number of participants at each time point is included in a legend below the figures.

Linear regression models adjusted for randomization strata are used to compare changes in CFRSD-CRISS and CFQ-R RSS between treatment groups. Least squares means and the treatment effect are presented along with corresponding 95% confidence intervals and p-values.

CFRSD-CRISS and CFQ-R RSS are also summarized at each study visit during the randomized period and as a change from Visit 1 and Visit 2. The differences between treatment groups are presented with accompanying 95% confidence intervals and p-values calculated using two-sample t-tests

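### SAP A.4 specifies no overdispersion correction for the Poisson (S)AE rate ratios, although one exacerbation can be recorded as several SAEs

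*SAP*

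**What the plan says.** SAP A.4 plans the (S)AE rate comparison in these words: "Poisson regression modeling is used to derive rate ratios and corresponding 95% confidence and to compare groups using a two-sided 0.05 level test". For system organ classes it adds: "Poisson regression is used to derive rate ratios and corresponding 95% confidence intervals comparing treatment arms for each SOC". No test is stated at that level. Protocol 15.4 has the matching sentence: "Poisson regression modeling will be used to derive rate ratios and corresponding 95% confidence". No scale parameter, robust variance, negative binomial model or collapsing of records into episodes is named in either document.

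Just before this, A.4 explains how exacerbations enter the database: "sites are asked to record the symptoms or physical findings associated with the pulmonary exacerbation as individual adverse events", and sites are also asked "to designate the seriousness of each of these events". Its own conclusion is: "Thus a single pulmonary exacerbation can be reported as several SAEs".

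A.4 also plans participant-level output: the difference in the proportion with at least one (S)AE (Newcombe-Wilson interval, Fisher's exact test), and histograms of counts per participant.

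For hospitalizations, exacerbations and antibiotic use, Protocol 15.4 says: "Event rates will be compared between treatment groups using Poisson regression". SAP A.6 does not repeat that model. It says "The number of pulmonary exacerbations and hospitalizations is descriptively summarized", and compares proportions by Fisher's exact test and Newcombe-Wilson intervals.

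**The concern.** Poisson regression with its default standard error takes the variance of a count to equal its mean. Two features of these data can break that. First, the recording rule lets one clinical episode add several records at once for the same participant. Second, AE counts usually differ between participants by more than Poisson variation, with or without exacerbations. In both cases the variance exceeds the mean and the default standard error of the log rate ratio is too small.

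What is at stake is the reading of the safety tables. Intervals would overstate certainty in either direction, and p-values would flag chance differences more than 5% of the time. Comparing safety profiles is a stated, exploratory objective, and SAP 1.2 places table shells for the DSMB reports in Appendix A. By SOC, where only intervals are planned, the issue is interval width.

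**Working it through.** **Inputs from the documents.** About 120 randomized 1:1, so 60 per arm (SAP 1.1); randomized follow-up of up to 6 weeks (SAP 1.1); two-sided 0.05 test (SAP A.4).

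**Inputs that must be assumed.** Event rates, records per episode and between-participant variance. The documents give none of these.

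**Formula.** If the variance is φ times the mean, the actual level of a nominal 5% Wald test is 2 × (1 − Φ(1.96/√φ)), and a correct interval is √φ times as wide on the log scale.

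**The plan's own figure first.** At φ = 1 the formula gives 0.050. Simulation of AEs at 1-3 per participant without extra variation gives 0.046-0.051. The nominal level is reproduced when the Poisson assumption holds.

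**Dispersion by scenario.**
- k records for every episode: φ = k.
- Variable records per episode: φ = E[k²]/E[k]. Uniform 1-3 gives (14/3)/2 = 2.33. One record with a quarter giving a second gives 1.75/1.25 = 1.4.
- A share p of records from episodes of k records, the rest single: φ = (1 − p) + pk. This is 1.3 at p = 0.3, k = 2 and 2.5 at p = 0.5, k = 4.
- AE mean μ with gamma variance v between participants: φ = 1 + vμ. This is 1.25 at μ = 1, v = 0.25 and 4 at μ = 3, v = 1.

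**Results.** The simulation used 40,000 trials per scenario, 60 per arm, equal follow-up, no true difference, and counted a zero-event arm as a non-rejection.

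| Assumed scenario | φ | Formula | Simulated level |
|---|---|---|---|
| AEs, mean 1-3, gamma variance 0.25-1 | 1.25-4 | 8.0%-32.7% | 7.9%-32.0% |
| All SAEs from 0.1-0.2 episodes per participant, 2 records | 2 | 16.6% | 14.6%-16.4% |
| Same, 3 records | 3 | 25.8% | 25.7%-26.6% |
| Same, 4 records | 4 | 32.7% | 32.9%-34.0% |
| Same, uniform 1-3 records | 2.33 | 20% | 18.1%-19.5% |
| Same, one record, a quarter giving a second | 1.4 | 9.8% | 6.9%-8.9% |
| 30%-50% of SAE records from episodes of 2-4, 0.1-0.2 SAEs per participant | 1.3-2.5 | 8.6%-21.5% | 4.9%-20.2% |

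**Sparse SAEs.** The formula is a large-sample one, and discreteness lowers the level when events are few. The result then depends on records per episode:
- 0.03 episodes per participant: 2.4%, 6.9% and 8.7% with 2, 3 and 4 records.
- 0.05 episodes per participant: 7.6%, 16.6% and 23.1%.
- Little clustering: 0.5% and 2.3% at those two rates when a quarter of episodes give a second record; 1.0%-4.8% for mixed sources at 0.05 SAEs per participant.

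**By SOC.** Coverage of the nominal 95% interval is about 97% at mean 0.1, 84%-95% at mean 0.3-1, and 79%-90% for 0.1-0.2 episodes of 2-3 records on a background of 0.2.

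**Protocol 15.4 event rates.** Each event is one record, so the effect is smaller: 0.4%-6% at mean 0.05-0.2 with gamma variance up to 1, and at most 11% at mean 0.3 with variance 2.

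**The remedy tested.** With a Pearson-scaled variance (t reference, 118 df) the level was at most 5.1% in every scenario. A sandwich variance reached 9.3% (mixed sources, half the records from episodes of four), so it is not the preferred choice.

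**The case against.** The strongest case against has four parts.

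**Silence is not a decision.** Appendix A is an overview that names a model family. A scaled Poisson model is still Poisson regression, so the text does not forbid it. This stands: a reader might infer that the plan rejects a dispersion term, but the documents show only that none is specified. The gap still matters, because the named model run as written gives the uncorrected standard error, and choosing the variance after seeing the data is what a plan should prevent.

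**Valid inference is already planned beside it.** The multiple-record practice is disclosed, and participant-level proportions, Fisher tests, histograms and SAE narratives are all planned. These are sound and unaffected by clustering. They answer a different question, however, and do not repair the rate-ratio interval or test.

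**The size is assumed.** This stands fully. The SAP says only that one exacerbation can produce several SAEs, with seriousness judged record by record. Entrants must be clinically stable and, azithromycin aside, free of IV or oral anti-pseudomonal antibiotics for four weeks (Protocol 6.2 and 6.3). An episode rate of 0.1 in 42 days is 0.1 × 365/42 = 0.87 per person-year, and 0.2 is 1.7, so the upper SAE figures may not be reached.

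**Sparse data make the test conservative.** This is true only when clustering is slight. With 3-4 records per episode the level exceeds 5% even at 0.03 episodes per participant.

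**Conclusion.** The point holds in conditional form. SAP A.4 and Protocol 15.4 base the (S)AE rate ratios, intervals and two-sided 0.05 test on Poisson regression without specifying an overdispersion correction, while A.4 itself describes a recording practice that can create overdispersion. Under the assumptions shown, the actual level is about 8%-32% for AEs and about 15%-34% for SAEs that all come from exacerbations with 2-4 records each. It is about 5%-20% when 30%-50% of SAE records come from episodes, and below 5% when SAEs are sparse and barely clustered.

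A reader might infer that every (S)AE test in the trial is anti-conservative, or that a trial decision is compromised. The documents support neither. The excess depends on unknown rates and clustering. AE rates are an exploratory endpoint (Protocol 5.2). SAP 1.3 sets no predetermined safety stopping rule, and its formal rule concerns FEV1 only. The primary analysis and the Fisher and Newcombe-Wilson comparisons are unaffected. The consequence is possible misreading of safety tables, which merits a correction because the correction is cheap.

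**What to change.** In SAP A.4, state that (S)AE rate ratios and intervals, overall and by SOC, come from Poisson regression with log follow-up time as offset and a Pearson-scaled (quasi-Poisson) variance, with the scale not allowed below 1. The floor matters because in sparse, unclustered SOCs (mean 0.05-0.1) the estimated scale fell below 1 in about 63%-83% of simulated trials, which would narrow the interval. Apply the same rule to any Poisson event-rate comparison kept from Protocol 15.4.

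Add a few-events rule. Where either arm has fewer than a stated number of participants with an event (for example, fewer than 5), base inference on the planned participant-level proportions and show the rate ratio descriptively. At 0.03 episodes per participant an arm has no event with probability exp(−1.8) = 0.165, so about 30% of trials yield no finite rate ratio.

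The cost is a few SAP sentences and a software option, with no new data. Protocol Section 15 leaves analysis detail to the SAP, so the protocol text can stand. Editing Protocol 15.4 itself would need Steering Committee agreement and IRB approval (Protocol 17.1). If the SAP is already final, SAP 2.3 provides for describing and justifying the deviation in the final report.

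The downside is intervals about √1.2 = 1.1 to √3.9 = 2.0 times as wide on the log scale at dispersion 1.2-3.9, and a conservative test when events are few. Without the floor it rejects about 0.4% of the time at 0.05 episodes per participant (about 3 per arm) and under 3% at 0.1 (about 6 per arm). The floor can only lower these figures.
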